6.2. Secondary analyses

Effects of cognitive training vs. PMR

- Treatment effects on the transfer task (n-back task) at follow-up assessment will be examined by estimating marginal means (and 95% CI) from the model above.
- Treatment effects on the training task (letter updating task) at post- and follow-up assessments will be analyzed using a linear mixed-effects model. This model will include the letter updating performance at post- and follow-up assessments (number of correctly recalled lists) as the dependent variable. Fixed effects will include group (cognitive training vs. PMR) and measurement time point (post vs. follow-up). Control covariates will include the letter updating performance at pre-assessment (number of correctly recalled lists), age, and sex. A random intercept for subjects will also be included. Immediate and sustained training effects at post- and follow-up assessments will be estimated via marginal means (95% CI) from this model.
- Treatment effects on the visuospatial memory task (virtual reality task) at post- and followup assessments will be analyzed using a linear mixed-effects model. This model will include the virtual reality task performance at post- and follow-up assessments (number of goals reached) as the dependent variable. Fixed effects will include group (cognitive training vs. PMR) and measurement time point (post vs. follow-up). Control covariates will include the virtual reality task performance at pre-assessment (number of goals reached), age, and sex. A random intercept for subjects will also be included. Immediate and sustained effects on visuospatial memory performance at post- and follow-up assessments will be estimated via marginal means (95% CI) from this model.
- Treatment effects on working memory discrimination (n-back task d'prime scores) at postand follow-up assessment will be analyzed using a linear mixed-effects model. This model will include the n-back d'prime scores at post-and follow-up assessments as the dependent variable. Fixed effects will include group (cognitive training vs. PMR), measurement time point (post vs. follow-up) and task difficulty (1-back vs. 2-back). Control covariates will include the n-back d'prime scores at pre-assessment, age, and sex. A random intercept for subjects will also be included. Immediate and sustained effects on working memory discrimination at post- and follow-up assessments will be estimated via marginal means

(95% CI) from this model.

- Treatment effects on health-related quality of life (PROMIS® PROPr scores) at post- and follow-up assessment will be analyzed using a linear mixed-effects model. This model will include the PROMIS® PROPr scores at post-and follow-up assessments as the dependent variable. Fixed effects will include group (cognitive training vs. PMR) and measurement time point (post vs. follow-up). Control covariates will include the PROMIS® PROPr scores at pre-assessment, age, and sex. A random intercept for subjects will also be included. Immediate and sustained effects on health-related quality of life at post- and follow-up assessments will be estimated via marginal means (95% CI) from this model.
- Treatment effects on subjective cognitive functioning (PROMIS® T-scores) at post- and follow-up assessment will be analyzed using a linear mixed-effects model. This model will include the PROMIS® cognitive functioning T-scores at post-and follow-up assessments as the dependent variable. Fixed effects will include group (cognitive training vs. PMR) and measurement time point (post vs. follow-up). Control covariates will include the PROMIS® cognitive functioning T-scores at pre-assessment, age, and sex. A random intercept for subjects will also be included. Immediate and sustained effects on subjective cognitive functioning at post- and follow-up assessments will be estimated via marginal means (95% CI) from this model.
- Treatment effects on the post-COVID functional status (PCFS total raw scores) at post- and follow-up assessment will be analyzed using a linear mixed-effects model. This model will include the PCFS total raw scores at post-and follow-up assessments as the dependent variable. Fixed effects will include group (cognitive training vs. PMR) and measurement time point (post vs. follow-up). Control covariates will include the PCFS total raw scores at pre-assessment, age, and sex. A random intercept for subjects will also be included. Immediate and sustained effects on post-COVID functional status at post- and follow-up assessments will be estimated via marginal means (95% CI) from this model.
- Treatment effects on the sleep efficiency levels (sleep efficiency percentage) at postassessment will be analyzed using a linear mixed-effects model. This model will include the sleep efficiency percentage at post-assessment as the dependent variable. Fixed effects will include group (cognitive training vs. PMR). Control covariates will include the sleep efficiency percentage at pre-assessment, age, and sex. A random intercept for subjects will also be included.

Effects of cognitive training with active vs. sham tDCS

We will use the same analytical approach to assess the effects of active versus sham tDCS on all outcomes, replacing the group effect (cognitive training vs. PMR) with the stimulation group variable (active vs. sham tDCS). The only exception will be the analysis of treatment effects on the training task (letter updating task), which will be examined using the following two linear mixed-effects models:

• The first model will assess the treatment effects on the training task (letter updating task) at training- and post- assessments. This model will include the letter updating performance across all training and post-assessments (number of correctly recalled lists in sessions from V2 to V11) as the dependent variable. Fixed effects will include the stimulation group (active vs. sham tDCS) and measurement time point (V2 to V11). Control covariates will include

the letter updating performance at pre-assessment (number of correctly recalled lists), age, and sex, along with a random intercept for subjects. Training and immediate post-assessment effects will be estimated through marginal means (95% CI) from this model.

• The second model will evaluate the treatment effects on the training task (letter updating task) at follow-up assessment. This model will include the letter updating performance at post- and follow-up assessments (number of correctly recalled lists) as the dependent variable. Fixed effects will include group (active vs. sham tDCS) and measurement time point (post vs. follow-up). Control covariates will include the letter updating performance at pre-assessment (number of correctly recalled lists), age, and sex. A random intercept for subjects will also be included. Sustained training effects at follow-up assessment will be estimated via marginal means (95% CI) from this model.

The choice of link function (logistic, linear, or ordinal) for all analyses will depend on the scale of the dependent variable. For skewed continuous data, we will apply appropriate transformations before analysis. In case of missing values, all secondary analyses will be done using the full analysis set with multiple imputed data. Per-protocol analyses will be conducted as sensitivity analyses. All secondary analyses will be conducted within an exploratory framework.

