1.3. Secondary hypotheses

• Cognitive training with either active or sham tDCS will result in greater improvements at post- and follow-up assessments compared to the control group (PMR) in post-COVID patients across multiple domains: (a) untrained working memory, measured by the percentage of correct responses on the n-back task (transfer task); (b) trained working memory, measured by the number of correctly recalled lists on the letter updating task; (c) visuospatial memory, measured by the number of goals reached on the virtual reality task; (d) working memory discrimination, measured by the d-prime scores on the n-back task; (e) health-related quality of life, measured by the preference-based scores (PROPr scores) on the Patient Reported-Outcomes Measurement Information System (PROMIS®) 29-Profile v2.1; (f) subjective cognitive functioning, measured by the T-scores on the PROMIS®

Cognitive Function Scale (short form 8a - v2.0); (g) post-COVID functional status, measured by the total raw scores on the Post-COVID Functional Scale (PCFS); and (h) sleep efficiency levels, measured as the percentage of time spent asleep relative to total time in bed, as recorded by an actigraphy device.

These outcomes will be assessed at post- and follow-up assessments, except for (a) untrained working memory, which will be evaluated only at the follow-up assessment, and (g) sleep efficiency levels, which will only be measured at the post-assessment.

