• Cognitive training with active tDCS will result in greater improvements at post and follow-up assessments compared to cognitive training with sham tDCS in post-COVID patients across multiple domains: (a) untrained working memory, measured by the percentage of correct responses on the n-back task (transfer task); (b) trained working memory, measured by the number of correctly recalled lists on the letter updating task; (c) visuospatial memory, measured by the number of goals reached on the virtual reality task; (d) working memory discrimination, measured by the d-prime scores on the n-back task; (e) health-related quality of life, measured by the PROPr scores on the PROMIS® 29-Profile v2.1; (f) subjective cognitive functioning, measured by the T-scores on the PROMIS® Cognitive Function Scale (short form 8a - v2.0); (g) post-COVID functional status, measured by the total raw scores on the PCFS; and (h) sleep efficiency levels, measured as the percentage of time spent asleep relative to total time in bed, as recorded by an actigraphy device.

These outcomes will be assessed at both post and follow-up assessments, except for the (g) sleep efficiency levels, which will only be measured at post-assessment.

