4.2. Secondary outcomes

Secondary outcomes will be assessed at both post-assessment and follow-up with specific exceptions indicated by an asterisk (*). These include:

- Untrained working memory performance, measured by the percentage of correct responses on the n-back task [(23) *at follow-up assessment].
- Trained working memory performance, measured by the number of correctly recalled lists on the letter updating task (24).

Statistical Analysis Plan

"Neuromodulation through brain stimulation-assisted cognitive training in patients with post-COVID-19 cognitive impairment (Neuromod- COV): study protocol for a PROBE phase IIb trial" Acronym: Neuromod-COV

- Untrained visuospatial memory performance, measured by the number of reached goals on the virtual reality task (25).
- Working memory discrimination, measured by the d-prime scores on the n-back task (23,26).
- Health-related quality of life, measured by the PROPr scores (27) on the PROMIS® 29-Profile v2.1 (28).
- Subjective cognitive functioning, measured by the T-scores on the PROMIS® Cognitive Function Scale [short form 8a v2.0; (28)].
- Post-COVID functional status, measured by the total raw scores on the PCFS (29).
- Sleep efficiency levels, measured as the percentage of time spent asleep relative to total time in bed, as recorded by an actigraphy device (*at post-assessment).

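### Does the subject random intercept in the sleep-efficiency model have to go, given that the outcome is taken only at post-assessment?

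*SAP*

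**What the plan says.** The sleep-efficiency bullet in SAP section 6.2 names a linear mixed-effects model. Its outcome is set by "This model will include the sleep efficiency percentage at post-assessment as the dependent variable", and group is the only fixed effect. The bullet goes on: "Control covariates will include the sleep efficiency percentage at pre-assessment, age, and sex. A random intercept for subjects will also be included".

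Section 4.2 defines the outcome as the share of time in bed spent asleep, "as recorded by an actigraphy device (*at post-assessment". Section 1.3 says the same for the training versus relaxation comparison, "sleep efficiency levels, which will only be measured at the post-assessment", and for the stimulation comparison, "sleep efficiency levels, which will only be measured at post-assessment". Table 1 (section 4.3) shows actigraphy at the pre and post visits and not at follow-up.

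The model is carried over to the stimulation comparison: "We will use the same analytical approach to assess the effects of active versus sham tDCS on all outcomes". The only stated exception is the letter updating task.

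Two closing statements in section 6.2 also bear on the point. On model form: "The choice of link function (logistic, linear, or ordinal) for all analyses will depend on the scale of the dependent variable". On status: "All secondary analyses will be conducted within an exploratory framework".

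**The concern.** All the other outcome models in sections 6.1 and 6.2 have at least two rows per participant: post and follow-up, and for the n-back models also two difficulty levels. A subject intercept belongs there. The sleep bullet drops follow-up and the time-point term but keeps the intercept, which looks like text carried over from the neighbouring bullets.

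If one value per participant is meant, the model contains a variance component that the data cannot estimate. One common R package stops with an error, and other programs report a split between the two variances that depends only on the program. The passage on link functions and transformations gives no rule for dropping a random effect. Multiple imputation does not help either, since each completed data set still has one row per participant. The sleep bullet also lacks the sentence, present in the other bullets of the training versus relaxation list, that names the estimate and interval to be reported.

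At stake would be an analysis that cannot be run as written, or one whose treatment estimate or standard error depends on the software.

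**Working it through.** The SAP gives no figure for this model. Its group sizes come from section 1.4: 40 in cognitive training (20 active, 20 sham) and 20 in relaxation.

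**1. Algebra for one row per participant.** Write y_i = x_i'β + u_i + e_i, with Var(u_i) = τ² and Var(e_i) = σ². With one row each, Var(y_i) = τ² + σ² and all covariances are zero, so V = (τ² + σ²)·I. The likelihood depends on τ² and σ² only through their sum. Generalised least squares with V proportional to I is ordinary least squares, so the group effect is the ANCOVA estimate. Its SE follows from the estimated sum, which equals the ANCOVA residual variance. A transformation of the outcome leaves this unchanged.

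**2. Numerical check, training versus relaxation (40 versus 20).** Simulated data with assumed values: pre value N(83, 7), slope 0.5, residual SD 6, age N(48, 11), binary sex. Residual df = 60 − 5 = 55.

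| Fit | Group effect | SE | Intercept / residual variance |
|---|---|---|---|
| Ordinary regression | 5.889 | 1.685 | none / 35.79 |
| R nlme | 5.889 | 1.685 | 31.37 / 4.41 |
| Python statsmodels | 5.889 | 1.685 | 17.89 / 17.89 |
| R lme4, default | refused | – | – |

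The log-likelihood was −189.963931 with 0, 25, 50, 75 or 99% of the variance given to the intercept. nlme reproduced the ANCOVA t-test on 55 df (p = 0.00094). The 95% CI is 5.889 ± 2.004 × 1.685 = 2.51 to 9.27.

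**3. Active versus sham (20 versus 20).** Residual df = 40 − 5 = 35. The group effect was 1.283, SE 2.040, in ordinary regression, nlme and statsmodels. The splits were 35.09/4.93 and 20.01/20.01 of a total of 40.03. The log-likelihood was −128.048754 at every split. lme4 refused again.

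**4. A second simulated data set (40 versus 20, other assumed values).** The REML log-likelihood was −133.1026 at all five splits. The group effect was 1.356 and the SE 1.504 by ordinary regression and at every split. statsmodels reported an SE of 1.502 with a Hessian warning, a difference of about 0.2%.

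**5. t or z reference.** A program that uses 1.96 gives an interval narrower by 1 − 1.960/2.004 = 2.2% (55 df) or 1 − 1.960/2.030 = 3.4% (35 df). That comes from the reference distribution and has nothing to do with the random intercept.

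**6. Imputation.** Each of the 30 completed data sets (section 5) gives the same estimate and variance under either model, so the pooled values agree as well.

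**7. Several nights per participant.** With five simulated nights (an assumed number; the SAP gives none) and no night term, the two variances separated: intercept 9.03, residual 23.5. A subject intercept needs repeated rows and does not need a night factor. When every participant has the same number of nights and all covariates are subject-level, the group effect also equals that of an ANCOVA on participant means.

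**The case for a change.** The strongest case for a change is that the bullet, read plainly, describes one percentage per participant and lists nothing that varies within a participant. A subject intercept is then meaningless. R is the only software the SAP names, so a refusal by lme4 is a realistic event. Either reading could be settled in one sentence at no cost, and whether nights enter singly or as a mean should not be chosen after seeing the data.

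Part of this stands. With one row the intercept is redundant, and the text does not say which reading is meant. The rest is weaker:

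- Sections 1.3 and 4.2 and Table 1 fix the assessment at which sleep is measured. They do not fix the number of values within it. The n-back outcome is likewise defined as a single percentage, yet section 6.1 models separate values for two difficulty levels.
- The SAP names R only for randomisation and sample size, and no package for the analyses. Two programs fit the model as written, so a departure from the text is not forced.
- Freedom to choose between nights and a mean has little to act on. The two agree when the numbers of nights are equal, and otherwise they differ only through weighting. Recording length and night-level handling of actigraphy are also details commonly left to the protocol.
- The missing reporting sentence leaves no real doubt. With one time point and one group factor, the adjusted group difference with its 95% CI is the only target, and the neighbouring bullets give the format.

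**Conclusion.** The observation about the variance components is correct if each participant contributes one value, but nothing is gained by amending the plan. On that reading the treatment effect and its SE are those of ANCOVA for both comparisons, apart from numerical differences of about 0.2% in one program's reported SE. The only quantity that varies materially between programs is a variance split that the SAP never plans to report. If several nights enter as rows, the model is sound as it stands. An analyst who meets the lme4 error would fit the equivalent regression and lose nothing.

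The equality with ANCOVA is algebraic and does not depend on the simulated values. It assumes a linear model, which suits a percentage treated as continuous. What remains is a gap in wording for one of eight secondary outcomes, in two exploratory comparisons. The primary analysis is not affected.

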6.3. Safety analysis

Safety outcomes will be reported as incidence (n & rates with 95% CI) both overall and by intervention groups, based on the safety analysis set. Incidence rates and corresponding 95% CIs will be estimated using Poisson regression models, which account for different observation periods across participants. Group comparisons will be conducted using incidence rate ratios and their 95% CIs. The safety analysis results will be interpreted and discussed comprehensively, including minor differences between groups.

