4.1.	Primary outcome	6
4.2.	. Secondary outcomes	6
4.3.	. Safety outcomes	7
5. H	Iandling of missing values	8
6. St	Statistical analyses	8
6.1.	. Primary analysis	9
6.2.	. Secondary analyses	9
6.3.	. Safety analysis	11
6.4.	. Example table of baseline characteristics	11

1. Study objective

A significant proportion of COVID patients experience persistent long-term symptoms (1-4), including cognitive deficits in attention, executive functions and memory (3,5,6). These cognitive impairments can impact daily living abilities, quality of life, and working capacity. Currently, there are no evidence-based treatment approaches for cognitive symptoms following post-COVID. Cognitive training interventions are a promising approach to counteract cognitive impairment (7-10). Moreover, transcranial direct current stimulation (tDCS) may enhance the effects of behavioral training, improve the consolidation of training outcomes, and facilitate transfer to other cognitive domains (11-13). However, the efficacy of cognitive training alone or in combination with tDCS on cognitive performance, quality of life, and mental health has not been evaluated in post-COVID patients with subjective or objective cognitive decline. The Neuromod-COV trial (14) aims to fill this gap by assessing the immediate and delayed effects of cognitive training, with or without concurrent tDCS, on cognitive performance, quality of life and mental health in patients experiencing post-COVID subjective or objective cognitive impairments.

The analyses described in this Statistical Analysis Plan will evaluate the efficacy of a threeweek cognitive training intervention with or without concurrent tDCS in patients with post-COVID cognitive impairments. This SAP has been prepared following the Guidelines for the Content of Statistical Analysis Plans in Clinical Trials (15). The trial will be reported following the Consolidated Standards of Reporting Trials [CONSORT (16)].

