2.1. Definitions

The **full analysis set** will consist of all randomized participants who received at least one day of intervention. If participants withdraw informed consent after baseline assessment, they will be considered screening failures and, therefore, will not be included in the full analysis set. The

per-protocol analysis set comprises all subjects who received the full three weeks of intervention or control intervention and completed all visits in the treatment groups they were allocated to. Safety outcomes [see Safety outcomes section (22)] are assessed during tDCS intervention, and all participants who received at least one intervention will be included in the safety analysis set according to their actual treatment. Since no participant received other treatment as intended or switched treatment groups during the study, and no information on safety measures is available for participants who missed intervention or follow-up visits or dropped out, the safety analysis set is the same as the per protocol analysis set in this study.

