4.3. Safety outcomes

Safety is assessed through an adapted (22) self-report questionnaire administered every third training day (V4, V7 and V10). This questionnaire asks participants to rate the intensity of various sensations, including itching, pain, burning, warmth/heat, metallic or iron taste, fatigue, decreased alertness, and others.

Table 1. Neuromod-COV outcome measures	. Adapted from Neuromod-COV	/ study protocol (14).
--	-----------------------------	------------------------

			Baseline	Pre (3 days before T1)	T1-T9 (9 sessions for 3 weeks)	Post (3 days after T9)	FU (1 month after Post)
			$\sim 3h$	~ 3h	~ 1h	~ 3h	~ 3h
Time point	Measurement	Mode	V0	V1	V2-V10	V11	V12
Enrollment							
Informed consent		Paper	Х				
Eligibility	Medical history	Paper	Х				
screening	Mini-DIPS (30)	Paper	Х				
Questionnaires	Demographics	Paper	Х				
Neuropsychological screening	VLMT (23) ROCF (31) DS (32) TMT(23) Stroop (33) PF (23) SF (23)	Paper	Х				
Intervention					← →		
Training tasks	Letter updating task (24)	Tablet-PC	Х	X	x ^a	Х	x
	PMR (18)	Instructed			x ^b		
Brain stimulation	tDCS (anodal vs. sham)	Device			х		

	Initial state questionnaire	Paper	X	Х	х	Х	Х
Quastiannairas	PANAS (34)	Paper			Х		
Questionnaires	Adverse events questionnaire ^c (22)	Paper			Х		
Additional assessm	nents						
Linturin ed te elve	n-back task (23)	Computer		Х		X ^d	Х
Virtual	Virtual reality task (25)	Computer		Х		Х	Х
	PROMIS® (29-Profile v2.1 & Cognitve functioning SF 8a v2.0; 28)	Paper		х		x	х
Questionnaires	Sleeping behavior: PSQI (35) ESS (36) MEQ (37)	Paper		x		x	х
	PCFS (29)	Paper		Х		Х	Х
General activity	Actigraphy	Device		х		Х	

T1-T9: trainings 1-9; FU: follow-up assessment; V0-V12: visits 0-12; Mini-DIPS: Brief Diagnostic Interview for Psychiatric Disorders; VLMT: German version of the auditory verbal learning test; ROCF: Rey-Osterrieth Complex Figure Test; DS: Digit Span Test; TMT: Trail Making Test. Stroop: Stroop Test; PF: Phonological fluency; SF: Semantic fluency; PMR: Progressive Muscle Relaxation; tDCS: transcranial Direct Current Stimulation.

PANAS: Positive and Negative Affect Schedule; PROMIS®: Patient-reported Outcome Measurement Information System; PSQI: Pittsburgh Sleep Quality Index; ESS: Epworth Sleepiness Scale; MEQ: Morningness-Eveningness Questionnaire; PCFS: Post-COVID Functional Scale.

^a Only for cognitive training groups.

^b Only for the PMR group.

^c Assessed every third training day (V4, V7 and V10).

^d Primary outcome

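### On-treatment symptom ratings are analysed as incidence with no pre-treatment reference, so any pre-existing low alertness or fatigue would inflate the rates and pull the rate ratios towards 1

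*SAP*

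**What the plan says.** SAP section 4.3 defines safety through a self-report questionnaire on which participants rate the intensity of "itching, pain, burning, warmth/heat, metallic or iron taste, fatigue, decreased alertness, and others". It is given at V4, V7 and V10 only. Table 1 agrees: the adverse events questionnaire is marked only in the training column. Section 2.1 likewise says that safety outcomes "are assessed during tDCS intervention".

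Section 6.3 then gives the analysis: "Safety outcomes will be reported as incidence (n & rates with 95% CI) both overall and by intervention groups". Rates come from Poisson regression, groups are compared by incidence rate ratios with 95% confidence intervals, and even small group differences are to be discussed. The section mentions no baseline covariate, no intensity threshold and no condition that a symptom be new or worse.

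On the population, section 1 says that many COVID patients "experience persistent long-term symptoms (1-4), including cognitive deficits in attention, executive functions and memory".

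Table 1 also lists an "Initial state questionnaire" at V0, V1, the training visits, V11 and V12. The SAP does not describe its items, its scale or when within a visit it is completed, and section 6.3 does not use it.

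**The concern.** Incidence means new events in people who did not have them before. An intensity rating taken only on treatment cannot separate a symptom that started or worsened under treatment from one the patient brought along. For local sensations such as itching or burning under the electrode this hardly matters. It matters for decreased alertness, given the attention deficits named in section 1, and plausibly for fatigue, although the SAP does not name fatigue as a post-COVID symptom.

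Two readings are at stake. The absolute rates could be taken as harm caused by training or stimulation when part of them is the underlying condition. And a real excess under active tDCS could look negligible on the ratio scale, because the same background is added to both numerator and denominator. The efficacy models in sections 6.1 and 6.2 all adjust for the pre-assessment value; the safety analysis has no counterpart.

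**Working it through.** The SAP states no rate or expected count for safety, so there is no figure of its own to reproduce.

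**Timing.** V2 to V10 are training sessions 1 to 9, so V4, V7 and V10 are sessions 3, 6 and 9. The first safety rating follows two completed sessions. A patient can contribute at most three reports per item.

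**Inputs for the illustration (all assumed).** Emergent risk per questionnaire: a1 = 0.20 (active) and a0 = 0.10 (sham), a true ratio of 2.0 and a true difference of 10 points. Background b = 0.20, 0.40 or 0.60, equal in both arms.

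**Any-report model.** A report is counted if the symptom is background or emergent, independently:
- counted proportion = 1 − (1 − b)(1 − a)
- difference = (1 − b)(a1 − a0)

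**Additive model.** Background and emergent rates add, as in a Poisson rate:
- ratio = (a1 + b)/(a0 + b)
- difference = a1 − a0

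| b | Any-report: active vs sham | Ratio | Difference | Additive: active vs sham | Ratio | Difference |
|---|---|---|---|---|---|---|
| 0 | 0.20 vs 0.10 | 2.00 | 10 points | 0.20 vs 0.10 | 2.00 | 10 per 100 |
| 0.20 | 0.36 vs 0.28 | 1.29 | 8 points | 0.40 vs 0.30 | 1.33 | 10 per 100 |
| 0.40 | 0.52 vs 0.46 | 1.13 | 6 points | 0.60 vs 0.50 | 1.20 | 10 per 100 |
| 0.60 | 0.68 vs 0.64 | 1.06 | 4 points | 0.80 vs 0.70 | 1.14 | 10 per 100 |

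**Absolute rates.** Against a true sham figure of 0.10, the counted figure is 2.8 to 6.4 times too high in the any-report model (0.28 to 0.64) and 3 to 7 times in the additive model (0.30 to 0.70).

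**Null case.** With a1 = a0, both ratios equal 1 for every b. Equal background creates no group difference in expectation.

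**Precision.** Section 1.4 plans 40 training participants, that is 20 per stimulation arm under 1:1 allocation, and 20 × 3 = 60 questionnaires per arm. Use the additive rates and SE(log ratio) = √(1/e1 + 1/e0), where e1 and e0 are the expected counts in the active and sham arms:
- b = 0: 12 vs 6 reports, SE = 0.500, ratio 2.00, 95% CI 0.75 to 5.33.
- b = 0.60: 48 vs 42 reports, SE = √(1/48 + 1/42) = 0.211, ratio 1.14, 95% CI 0.76 to 1.73.

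The background reports narrow the interval around a diluted ratio, and in the second case the upper limit falls below the true ratio of 2.0. This treats reports as independent, which repeated reports from one chronically symptomatic patient are not.

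**The case against.** The strongest reply is that section 6.3 never defines an event. The questionnaire is an adapted form that is not shown. It may ask about sensations during stimulation, about onset or about attribution, and a sensible analyst might exclude long-standing symptoms. This stands in part. A reader might infer that the plan definitely counts every tired patient as an incident case; the text does not say so. What it does say is that on-treatment intensity ratings become incidence and rate ratios with no reference stated, and under that text such counting is permitted.

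The reply also has force on the background. Fatigue is not named in the SAP as a symptom of the condition, a deficit in attention is not the same as decreased alertness, and no prevalence is given. The 20% to 60% range is therefore an assumption about these patients, not a finding.

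Randomisation with a double-blind sham comparison protects against a false signal between the stimulation arms in expectation, and section 6.3 shows rates by group as well as ratios, so a high background would be visible. That stands, but a visible high rate does not tell the reader how much of it is emergent.

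One might also think that a rate difference removes the background altogether. It does so only in the additive model; in the any-report model the 10 points shrink to 8, 6 and 4.

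**Conclusion.** The point holds for decreased alertness and, plausibly, fatigue. As written, section 6.3 yields on-treatment prevalence plus any emergent symptoms, under the name of incidence. If background exists and is similar across arms, absolute rates are too high and the expected ratio lies closer to 1 than the true one.

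The direction follows from the arithmetic for any background above zero; the size cannot be derived from the SAP. In the illustration a true ratio of 2.0 appears as 1.29 to 1.06 or as 1.33 to 1.14, depending on the model. With about 20 patients per arm, chance imbalance in background could move a single observed ratio either way; attenuation is the expected direction only.

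A reader might infer that the safety analysis as a whole is invalid or that a harm will be hidden. The documents do not support that: most listed sensations are little affected, a true ratio of 1 stays 1, and the primary analysis and sample size are untouched. Nor can it be assumed that a usable baseline already exists, because the content and within-visit timing of the initial state questionnaire are not described.

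**What to change.** In section 6.3, for decreased alertness and fatigue (and any other item that may pre-exist), define an event as a rating that is new or worse than the patient's own pre-treatment or pre-session rating. Take that rating from the initial state questionnaire where it contains the item, and state the visit used and the change that counts as worse. Report the crude counts alongside.

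If the initial state questionnaire does not contain the item, report it as on-treatment symptom prevalence, not incidence. Show absolute proportions and their difference by arm next to the ratio, with a note that the difference may be attenuated as well.

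The cost is SAP wording and, if the item was collected, one derived variable. If it was not, only the labelling and presentation can change. The downside of the new-or-worse definition is fewer events and wider intervals for these items.
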